#### Humoral response

For all the humoral assays the immune response values will be  $\log_{10}$ -transformed before any further handling. The  $\log_{10}$ -transformed values will be used throughout the analysis. In the graphs, original values will be displayed on the  $\log_{10}$  scale.

For each assay and at each time point geometric mean of actual values, geometric mean increases and percentage of responders, all with corresponding 95% CIs will be provided by group in the tables. Within each group, the mean fold change of Week 52 to Week 72 will be reported. The definition of responders is defined in section 6.4. for each assay. Graphical presentations will be provided displaying dots for the subject values and including the geometric mean and the percentage of responders. If available, baseline values will be summarized pooling all the groups and will be displayed on the left of each graph. Data from post-baseline timepoints will be plotted next to each other for each group, a symbol will identify the geometric mean (or the median) of each group and timepoint.

In the graphs the actual values will be shown and the LLOQ cut-off will be visualized, the values below LLOQ or below LOD will be visualized with the value imputed as described in section 6.3.

Graphs by subgroups listed in section 2.4 will be done for ELISA (Clade C C97ZA.012, Mos1) and for ADCP (Clade C C97ZA.012), Mos1).

Durability will be displayed as a line plot showing the GM/median for each vaccine regimen.

Magnitude-breadth (MB) plot for the ELISA assay will be provided at post-baseline timepoints to explore the magnitude and breadth of each individual serum sample assayed (antibody titers of 5 Clades). MB curves will show, for each possible titer threshold, the proportion of antibody titers greater than this threshold. The group-specific curve obtained as the average MB across all subjects in that group will be displayed. The AUC-MB is calculated as the average of the titers over the panel of antigens.

For BAMA the median will be reported instead of the geometric mean. Cumulative number of responses across the IgG/antigen classes will be tabulated.

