**6.4. Handling of Missing and/or Invalid Immune Response Data**

Analysis will be carried out on the available data, no imputation will be done for missing samples. BAMA and ICS unreliable values should be excluded from the analysis: those records will be flagged in the SDTM dataset.

LLOQs by assay/test are listed in section 6.5. Values below LLOQ or LOD will be handled as follows:

- Calculation of Geomean (humoral response except ADCP) and median (cellular response):
  - o values < LLOQ are imputed =LLOQ/2
  - o values = LOD are imputed =LLOQ/2

For ADCP only:

- o values < LOD are imputed =LOD/2

- Calculation of fold increases from baseline:
  - o values <LLOQ are imputed =LLOQ
  - o values =LLOQ are imputed = LLOQ

For ADCP only:

- o values < LOD are imputed =LOD

Values above the upper limit of quantification (ULOQ) will be handled as follows:

- Calculation of geomean and median:
  - o Values>ULOQ are imputed=ULOQ.
- Calculation of fold increases from baseline:
  - o Values >ULOQ are imputed with ULOQ

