**6.5. Immune response assays: details**

The details for each immune response assay are listed in following table. The final framework will be reported in the DPS, as not all details might be available at the time this SAP has to be approved.

Assay	Test	Lab	LLOQ a	LOD a	ULOQ a	Unit	Responder definition/Positivity (if baseline is not available)
ELISA	Ad26 VNA	Janssen Vaccines and Prevention	17	NA	NA	IC90	>LLOQ
Env ELISA IgG-t gp140	Clade A (92UG037.1) Clade B (1990a) Clade C (Con C) Clade C (C97ZA.012) Mos1	Janssen Vaccines and Prevention	625 156.25 625 156.25 78.125	0	1600000 800000 1600000 1250000 1250000	EU/ml	1) if baseline <LLOQ or missing, R>LLOQ 2) if baseline >=LLOQ, R=3-fold increase from baseline
Env ELISA IgG1-3	Clade C (C97ZA.012) IgG1 Clade C (C97ZA.012) IgG3	BIDMC	12.3 12.4	4	403.4 120.8	EC50	
Env ADCP gp140	Clade A (92UG037.1) Clade B (1990a) Clade C (Con C) Clade C (C97ZA.012) Mos1	Ragon	NA	5.16 6.43 6.49 4.32 4.28	NA	PS	1) if baseline <LOD or missing, R>LOD 2) if baseline >=LOD, R=3-fold increase from baseline
VNA	TZM-bl Clade B (6535.3) TZM-bl Clade B (BZ167.12) TZM-bl Clade B (Bx08.16) TZM-bl Clade B (SF162.LS) TZM-bl Clade B (SS1196.1)	Seaman (BIDMC)	20	NA	43740	ID50	>LLOQ
TZM-bl b	Clade C (MW965.26) Clade C (97ZA012.12) b Clade C (ZM233M) Clade C (CE703010010) Clade C (2759058)	Duke U	10	NA	21870	ID50	>LLOQ

a In case final LLOQ and ULOQ values present in the dataset differ from those listed in this table, those provided from the lab should be used.

b At Week 52 samples that have a titer >500 against MW965.26 or >50 against 97ZA012.12 at Week 28 will be assayed against ZM233M, CE703010010, 2759058, ZM215F, SO431, CE704810053.  
Samples that have a titer >50 against MW965.26 at visit 15 (Wk52) will be assayed against MW965.26 at visit 17 (Wk72). Samples that have a titer >10 against 97ZA012.12 at visit 15 (Wk52) will be assayed against 97ZA012.12 at visit 17 (Wk 72).

Assay	Test	Lab	LLOQ a	LOD a	ULOQ a	Unit	Responder definition/Positivity (if baseline is not available)
	Clade C (ZM215F) Clade C (SO431) Clade C (CE704810053)						

BAMA IgG3	HIV ENV Con S gp140 CFI (Clade M) HIV ENV Con 6 gp120/B (Clade M) HIV ENV gp41 HIV ENV 1086C_D7gp120 (Clade C) HIV ENV 1086C gp140 (Clade C) HIV ENV 1086C_V1V2 (Clade C) HIV ENV gp70_B.Case A_V1V2 (Clade B)	Duke U	100 e	NA	NA	MFI	BAMA interpretation= 1

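### Clade C TZM-bl results at the triggered visits come only from subjects above an earlier titre cut-off, and the SAP has no rule that separates these untested samples from missing ones or labels the summaries as conditional

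*SAP*

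**What the plan says.** Footnote b to the TZM-bl entry in SAP 6.5 sets three testing rules.

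- MW965.26 at Week 72: "Samples that have a titer >50 against MW965.26 at visit 15 (Wk52) will be assayed against MW965.26 at visit 17 (Wk72").
- 97ZA012.12 at Week 72: "Samples that have a titer >10 against 97ZA012.12 at visit 15 (Wk52) will be assayed against 97ZA012.12 at visit 17 (Wk 72").
- Six further Clade C viruses at Week 52: "At Week 52 samples that have a titer >500 against MW965.26 or >50 against 97ZA012.12 at Week 28 will be assayed against ZM233M" and five others.

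The word 'only' is not used, but the conditions have no purpose unless samples that fail them are left untested. For the Clade C panel the LLOQ is 10, and a responder has a titre above the LLOQ.

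SAP 6.3 asks for group summaries of every humoral assay: "For each assay and at each time point geometric mean of actual values, geometric mean increases and percentage of responders", with 95% CIs. It also asks for a Week 52 to Week 72 fold change within each group, and a durability line plot whose assays are not named. On absent results, SAP 6.4 says: "Analysis will be carried out on the available data, no imputation will be done for missing samples". For values below the LLOQ it gives "values < LLOQ are imputed =LLOQ/2" for GMs and "values < LLOQ are imputed =LLOQ" for fold increases from baseline. It does not say which applies to the Week 52 to Week 72 contrast. On assay details SAP 6.5 adds: "The final framework will be reported in the DPS".

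**The concern.** A sample left untested because of a low earlier titre is absent for a reason tied to the outcome. If it is treated as an ordinary missing sample, the table row carries the group's name but describes a selected part of the group. With positive correlation between titres, the GM and the responder rate are too high for the group.

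Durability is affected in two opposite ways. An unpaired line compares everyone at Week 52 with a selected subset at Week 72, so it understates waning. A paired fold change in tested subjects starts from values selected for being high. Regression to the mean then overstates waning. Without a label, a reader could not reconcile the two. Neutralising antibody titre and breadth is a secondary endpoint (Protocol 2.1).

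**Working it through.** The documents state no TZM-bl figure to reproduce, so the check is an illustration.

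**Inputs from the documents.** Cut-offs 50 and 10 at Week 52; 500 and 50 at Week 28; LLOQ 10; responder above 10; LLOQ/2 = 5 for GMs. The log10 SD of 0.4 comes from Protocol 11.3, where it refers to binding titres.

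**Assumptions.** Bivariate normal log10 titres at Weeks 52 and 72; correlation 0.7; true decline 2-fold for MW965.26 and 0.2 log10 for 97ZA012.12; the Week 52 medians shown. There were 2,000,000 simulated subjects per setting.

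**Formulas.** With T the tested set, reported GM = 10^mean(log10 titre over T) and reported responder rate = responders in T / n(T). The true values use everyone. Line ratio = Week 72 GM / all-subject Week 52 GM. Paired ratio = GM of each subject's Week 72/Week 52 ratio.

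MW965.26:

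| Week 52 median | Tested | Week 72 GM, true vs reported |
|---|---|---|
| 50 | 50% | 24 vs 41 |
| 100 | 77% | 49 vs 64 |
| 250 | 96% | 125 vs 132 |
| 500 | 99% | 250 vs 253 |

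The line ratio is 0.84 (41/49) against a true 0.49 (24/49) at median 50, and 0.53 against 0.50 at median 250. At median 50 the reported GM runs from 35 to 48 over correlations 0.5 to 0.9.

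97ZA012.12 responders at Week 72:

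| Week 52 median | Tested | All subjects | Tested subset | Untested as non-responders |
|---|---|---|---|---|
| 10 | 50% | 31% | 52% | 26% (0.50 × 52%) |
| 25 | 84% | 69% | 78% | 65% (0.84 × 78%) |
| 50 | 96% | 89% | 92% | 88% (0.96 × 92%) |

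**Paired ratio, like for like** (everyone tested vs tested subset, same below-LLOQ rule on both sides):

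| Virus, Week 52 median | Below LLOQ = LLOQ/2 | Below LLOQ = LLOQ |
|---|---|---|
| MW965.26, 50 | 0.49 vs 0.40 | 0.53 vs 0.40 |
| 97ZA012.12, 10 | 0.73 vs 0.48 | 0.83 vs 0.67 |
| 97ZA012.12, 25 | 0.63 vs 0.55 | 0.70 vs 0.64 |
| 97ZA012.12, 50 | 0.62 vs 0.60 | 0.65 vs 0.64 |

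The subset's decline is steeper in every row, under either rule.

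**Six-virus panel.** Assume 29% true responders, cross-virus correlation 0.5 and a Week 28 97ZA012.12 median of 10. At Week 28 MW965.26 medians of 250, 500 and 1000, 24%, 50% and 77% are tested, and 55%, 43% and 35% of those respond. Counting untested as non-responders gives 13% (0.24 × 55%) and 27% (0.77 × 35%) at the two ends.

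**The case against.** The testing rule is disclosed in the SAP. The data presentation specification (DPS), which is not available here, may settle denominators and labels. Nothing says that the number tested will be left out. The planned 95% CIs widen and the subject-level dots thin out as fewer are tested. Every titre setting above is assumed. The Protocol (1.1.2.2) reports the Week 72 analysis as done, and the SAP introduction says those outputs will not be repeated.

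Most of this stands, and it keeps the point small. It does not remove it: wider intervals and fewer dots do not show why subjects are absent, and the SAP does not say that the DPS will cover this.

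A reader might also infer more than the documents support:

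- *That the rows describe earlier responders.* This fits only 97ZA012.12, whose cut-off equals the responder definition. For MW965.26, Week 52 responders with titres of 11 to 50 are also untested. The six-virus panel is selected on two other viruses.
- *That the direction of the paired 97ZA012.12 bias depends on the below-LLOQ rule.* This comes from setting a censored ratio against the uncensored decline of 0.63 (10^-0.2). Compared like for like, the decline is steeper under both rules.
- *That a primary endpoint or planned comparison is compromised.* SAP 1.3 plans no formal hypothesis test. TZM-bl is not among the assays listed for comparison in SAP 6.3, and the Clade B panel has no such condition.

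**Conclusion.** The point holds as a minor one. Followed as written, SAP 6.3 and 6.4 give GMs and responder rates at the triggered visits that apply only to subjects above the cut-off, and that are biased upward for the group if titres are positively correlated. A TZM-bl durability line, if one is drawn, would understate waning. The paired Week 52 to Week 72 fold change overstates it for both viruses.

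The size cannot be found from the documents. It is negligible if nearly all subjects pass the cut-off and large if many fail. The illustration rests on a borrowed SD and on assumed medians, correlations and declines. Only descriptive Clade C TZM-bl summaries of a secondary endpoint are affected.

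**What to change.** In SAP 6.4, flag samples not assayed under footnote b separately from missing samples. Then, for each triggered virus and visit in the active groups:

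1. Report the number tested out of the number of eligible samples. Eligible means after SAP 2.3.2 has removed samples taken after Week 48 from subjects whose fourth dose was missed or out of window.
2. Give the responder rate over all eligible samples with untested counted as non-responders (a lower bound). Beside it, give the tested-subset rate labelled as conditional on the earlier titre. Each needs its 95% CI.
3. Do not present the pair as a range certain to hold the true rate. In simulated groups of 22 (the Group 1 evaluable number in Protocol 11.3), the full-sample rate exceeded the tested-subset rate in about 1% to 14% of trials across the three 97ZA012.12 settings.
4. In any TZM-bl durability line, use the same subjects at Weeks 52 and 72.
5. Label the GMs and fold changes as conditional, and state the below-LLOQ rule for the Week 52 to Week 72 fold change.

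For placebo, report the number tested, with no rate or upper limit if none were tested.

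Because Week 72 outputs are not repeated, a short labelled addendum is enough. The cost is SAP wording, one derivation flag, a little extra analysis and less favourable figures. No new assays are needed.

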**7. SOCIAL IMPACT QUESTIONNAIRE**

Data from the Vaccine Research Center (VRC) Social Impact Questionnaire will be summarized using descriptive statistics.

**8. VECTOR SHEDDING ASSESSMENTS**

A listing of participants with positive AD26 vector shedding PCR result will be provided. The listing will include all samples available, assay and site.

**APPENDIX 1: LABORATORY, VITAL SIGNS AND ABNORMALITY GRADINGS**

LABORATORY A				
PARAMETER	GRADE 1 MILD	GRADE 2 MODERATE	GRADE 3 SEVERE	GRADE 4 POTENTIALLY LIFE-THREATENING
HEMATOLOGY				
Absolute Neutrophil Count (ANC)	800 x 10  – 1.000 x 10  /L	0.600 x 10  – 0.799 x 10  /L	0.400 x 10  – 0.599 x 10  /L	<0.400 x 10  /L
Hemoglobin (Hgb) (HIV NEGATIVE ONLY) Male Female	10.0 – 10.9 g/dL 9.5 – 10.4 g/dL	9.0 – 9.9 g/dL 9.4 – 8.5 g/dL	7.0 – 8.9 g/dL 8.4 – 6.5 g/dL	<7.0 g/dL <6.5 g/dL
Platelets, decreased	100.000 x 10  – 124.999 x 10  /L	50.000 x 10  – 99.999 x 10  /L	25.000 x 10  – 49.999 x 10  /L	<25.000 x 10  /L
WBC, decreased	2.000 x 10  – 2.500 x 10  /L	1.500 x 10  – 1.999 x 10  /L	1.000 x 10  – 1.499 x 10  /L	<1.000 x 10  /L
CHEMISTRIES				
ALT (SGPT)	1.25 – 2.5 x ULN	2.6 – 5.0 x ULN	5.1 – 10.0 x ULN	>10.0 x ULN
AST (SGOT)	1.25 – 2.5 x ULN	2.6 – 5.0 x ULN	5.1 – 10.0 x ULN	>10.0 x ULN
Creatinine	1.1 – 1.3 x ULN	1.4 – 1.8 x ULN	1.9 – 3.4 x ULN	≥ 3.5 x ULN
URINALYSIS				
Hematuria	6-9 RBV/HPF	≥10 RBV/HPF	Gross, with or without clots or with RBC casts	Transfusion indicated
Proteinuria, random collection	1+	2+	3+ or higher	NA

a This list is restricted to the laboratory parameters collected in this study for which a DAIDS 2.0 grading is available. Only ranges applicable for adults are reported. For a complete list refer to the CTP appendix 1.

VITAL SIGNS					
PARAMETER	UNIT	GRADE 1	GRADE 2	GRADE 3	GRADE 4
Temperature a	°C	≥38.0 - <38.5	≥38.6 - <39.2	≥39.3 - <39.9	≥40.0
Hypertensiona					
Systolic Blood Pressure	mmHg	≥140 - <159	≥160 - <179	≥180	NA
Diastolic Blood Pressure	mmHg	>90 - <99	≥100 - <109	≥110	NA
Hypotension	mmHg	NA	NA	NA	NA
Pulse ratea					
Tachycardia	bpm	≥101 - <115	≥116 - <130	>130	NA
Bradycardia	bpm	≥50 - <54	≥45 - <49	<45	NA

a DAIDS 2.0 grading, see also CTP appendix 1
